#### **4.2. Selection of Key Secondary Efficacy Endpoints.**

The AUC of the pulmonary, cardiovascular, local wound, hematologic symptoms, renal, and nervous system sections of the SSS from baseline through Day 7 will provide a comprehensive measure of snakebite envenoming pathology through the first week. This outcome differs from the primary outcome because it includes the local wound score, which is an important component of snakebite envenoming pathology in both the U.S. and India. Also, by covering the 7-day period following randomization, it will enable the assessment of benefits of varespladib on the resolution of toxicity in different organ systems occurring at different time points within the first week.

Total antivenom administration from Baseline through Day 28 is an important secondary outcome. Administration of antivenom by clinicians is based on illness severity and clinical status over time: Patients who continue to manifest toxicity will typically receive additional doses. Antivenom has medical risks, including both hypersensitivity reactions and serum sickness. Moreover, antivenom is expensive and in many settings in both the U.S. and India there is limited availability of antivenom (e.g., many small emergency departments in the U.S. do not stock antivenom). If sPLA2 inhibition with varespladib reduces the need for antivenom, that would indicate a more rapid improvement in the patient's clinical condition, and be important to both patients and healthcare systems.

Pain is an important clinical manifestation of snakebite envenoming. While snakes use venom primarily for predation and defense, venom sPLA2 toxins directly affect or potentiate the action of other venom toxins to activate mammalian sensory neurons and cause enhanced pain (Kazandjian et al., 2021). In the U.S., bites from the common venomous snake species (*Agkistrodon spp.* and *Crotalus spp.*) often result in severe pain. Pain is not only a cause of immediate suffering, pain also correlates with tissue injury and short-term disability and predisposes patients to persistent symptoms and delays in return to work. Evidence that varespladib reduces pain symptoms in humans following snakebite envenoming would provide important evidence of efficacy that is distinct from the primary and other key secondary

endpoints.

The CGI-I provides a global summary of a patient's improvement from the clinician's perspective. This global summary has the potential to integrate information about improvements in multiple organ systems, which is valuable because of the complex and heterogeneous pathology of snakebite envenoming. The investigators who are participating in the trial have extensive experience caring for patients bitten by venomous snakes and will be able to evaluate accurately what constitutes a meaningful improvement.

#### **4.3. Interim Analysis and Data Monitoring**

No interim efficacy analyses are planned.

The data safety monitoring board (DSMB) operates under a charter that was finalized prior to the start of the study. The DSMB evaluates the safety data at the intervals specified in the DSMB charter. In case of significant toxicity, the DSMB may choose to review the available safety data and recommend stopping recruitment. If toxicity is observed, the treatment assignment for the subject(s) involved may be unblinded by the DSMB at its discretion.

### **5. Analysis Populations**

The following analysis populations are planned for this study:

- **Safety Population (SAF):** The Safety Population includes all subjects who receive any amount of IP. Subjects who are members of the SAF population will be analyzed according to the treatment received. This population will be used for analysis of demographics, baseline characteristics, and all safety analyses.
- **Intent-To-Treat Population (ITT):** The ITT population includes all subjects who have been randomized. Subjects included in the ITT population will be analyzed as randomized. The ITT population will be used for analysis of demographics, baseline characteristics, and all efficacy analyses.\*
- **Per-Protocol Population (PP):** The PP population includes all subjects in the ITT without any significant protocol deviation. Subjects who are members of the PP population will be analyzed as randomized. This will be a secondary supporting population for the primary efficacy analyses.\*
- **Pharmacokinetic Population (PK):** The PK Population includes all subjects in the SAF Population who provide at least 1 evaluable post-dose PK measurement. Subjects who are members of the PK population will be analyzed according to the treatment received.\*

\*Assignment of subjects to populations will be confirmed at a blinded data review meeting to be held before the study database is locked.

### **6. General Issues for Statistical Analysis**

#### **6.1. Statistical Definitions and Algorithms**

Prior to analyses, lab values will be standardized to consistent units.

### **6.1.1. Baseline**

Observations recorded before or immediately after the first dose of treatment will be used as the baseline observation for all calculations of change from baseline.

### **6.1.2. Adjustments for Covariates**

The comparison of the primary and secondary efficacy endpoints between the varespladib-methyl and placebo groups for the primary efficacy analysis will be adjusted for four variables: (1) baseline SSS composed of the pulmonary, cardiovascular, hematologic, renal, and nervous system sections treated as a continuous variable; (2) age group treated as a dichotomous variable (age 5-17 vs. age  $\geq$ 18 years); (3) baseline neurotoxicity (SSS neurological system subscore) treated as a dichotomous variable (0-1 vs.  $\geq$ 2); and (4) Country (U.S. vs. India). Because we anticipate low numbers of patients in the two pediatric age group strata, we have collapsed these two strata into a single group (age 5-17) for the purpose of data analysis. A sensitivity analysis for the primary and key secondary endpoints will include a fourth covariate: completion of the initial dose of antivenom prior to initiation of study drug (Yes or No).

The mixed model for repeated measurements (MMRM) will be adjusted for baseline SSS, baseline neurotoxicity, age group, completion of the initial dose of antivenom prior to initiation of study drug, and scheduled timepoint of assessment. It will also include terms for treatment-by-time interaction and baseline score-by-time interaction.

The Cox model to estimate the hazard ratios for all-cause mortality will be adjusted for baseline SSS, baseline neurotoxicity, age group, and completion of the initial dose of antivenom prior to initiation of study drug.

### **6.1.3. Multiple Comparisons**

A gatekeeping or fixed-sequence procedure will be used for testing the key secondary endpoints. See details in [Section 8.1.2](#).

### **6.1.4. Handling of Dropouts or Missing Data**

For the primary efficacy analysis, subjects with a missing SSS at either 6- or 9- hours will be given an “average” SSS at 6 and 9 hours equal to the single score that is available from this time period. For subjects with missing SSS’s at both 6 and 9 hours, the site investigator will be asked to use all available contemporaneous clinical and laboratory data to determine the SSS at these time points. These scores will be obtained and finalized prior to database lock to ensure that investigators are blinded during this process. Finally, if missing data persists after the prior methods, then multiple imputation will be performed based on country, gender, baseline age, baseline SSS scores, treatment assignment, and available post-baseline SSS scores. Subscores

will be imputed and then the SSS score will be derived. More details on the multiple imputation process are provided in [Section 6.1.4.1](#) below.

For the first key secondary endpoint, AUC of the SSS through Day 7, for any missing data, the site investigators will again be asked to use all available contemporaneous clinical and laboratory data to determine the SSS at these time points. If data are still missing, multiple imputation will be used to determine missing scores and subscores based on country, baseline age, gender, baseline SSS scores, treatment assignment, and available post-baseline SSS scores. More details on the multiple imputation process are provided in [Section 6.1.4.1](#) below.

For the second key secondary endpoint, total antivenom administration, if the patient has complete data on antivenom administration through Day 3, then no change will be made to the total antivenom administered. This decision reflects the fact that in clinical practice in the U.S. and India, antivenom administration after 48 hours is uncommon. If the patient is missing data prior to Day 3, then the treatment of missing data will depend on the reason for missingness. If the patient has been discharged from the hospital, then no changes will be made to the available total amount of antivenom administered. If the patient has missing data prior to Day 3 and has not been discharged from the hospital or is transferred to another hospital, we will review each case and based on the patient's SSS will determine if the patient met criteria of additional antivenom. If the patient did meet criteria for additional antivenom, then we will assume a single additional dose was given to the patient, with the number of vials in this dose corresponding to the standard treatment dose in the region where the patient is receiving care.

For the third key secondary endpoint, AUC of the NPRS through Day 3, multiple imputation will be used to replace missing scores based on country, baseline age, gender, baseline NPRS scores, treatment assignment, and available post-baseline NPRS scores. More details on the multiple imputation process are provided in [Section 6.1.4.1](#) below.

For the fourth key secondary endpoint, CGI-I at Day 2, multiple imputation will be used to model missing values; with more details in [Section 6.1.4.1](#) below.

Individuals who cannot respond to patient-reported assessments due to severity of snakebite envenoming will be given a score corresponding to the worst score available in the assessment. Specific assessments and unable to respond scores are:

- PSFS = 0 (Unable to perform activity)
- PGIC = 10 (Feel much worse)
- Grip Strength = 0

A tipping point analysis will be conducted as a sensitivity analysis to handle missing data for the primary efficacy endpoint. More details are provided in [Section 6.1.4.3](#) below.

For the key secondary efficacy endpoints, a sensitivity analysis to handle missing data will be conducted only if results cannot be calculated for more than 10 study participants. In this case, the nature of the sensitivity analysis will be determined on review of the data.

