10.2.3.5 Day 1 (5 to 6 Hours)

Measure vital signs per institutional practice

OPX-PR-01

 Perform individual assessments pertaining the SSS, prior to administration of repeat doses of antivenom, if required (clinical evaluation of the actual SSS point score will be performed after completion of the study):

- Local wound severity
- Pulmonary severity
- Cardiovascular severity
- Gastrointestinal severity
- Hematologic severity
- Renal severity
- Nervous system severity
- Measure Head-Lift duration (0 to 5 seconds)
- Perform NPRS
- Measure grip strength
- Collect blood and urine for the following laboratory assessments:
 - CBC
 - Serum chemistry
 - LFTs
 - Hemolysis (Free hemoglobin, haptoglobin, LDH)
 - PT, PTT, thrombin time, INR
 - Absolute fibrinogen
 - CK
 - sPLA₂ levels at 6 hours post-dose as described in Section 10.2.1
- Record concomitant medications and therapies (e.g., prescription and nonprescription medications, pain medications)
- Perform CGI-I
- Perform PGIC
- In sedated, endotracheally intubated subjects, perform additional assessments according to instructions in Section 10.3.1.7.
- Collect PK samples from subset of subjects as described in Section 10.3.2.1
- Continue SOC treatment
- Record hospitalization details

OPX-PR-01

- Record pulmonary support interventions
- Assess and record AEs

10.2.3.6 Day 1 (8 to 10 Hours)

- Measure vital signs per institutional practice
- Perform individual assessments pertaining the SSS, prior to administration of repeat doses of antivenom, if required (clinical evaluation of the actual SSS point score will be performed after completion of the study):
 - Local wound severity
 - Pulmonary severity
 - Cardiovascular severity
 - Gastrointestinal severity
 - Hematologic severity
 - Renal severity
 - Nervous system severity
- Measure Head-Lift duration (0 to 5 seconds)
- Perform NPRS
- 12-lead ECG
- Measure grip strength
- Collect blood and urine for the following laboratory assessments:
 - CBC
 - Serum chemistry
 - Hemolysis (Free hemoglobin, haptoglobin, LDH)
 - PT, PTT, thrombin time, INR
 - Absolute fibrinogen
 - CK
 - sPLA₂ levels as described in Section 10.2.1
 - Biomarkers (CRP, and D-dimer)
- Perform CGI-I
- Perform PGIC

OPX-PR-01

• In sedated, endotracheally intubated subjects, perform additional assessments according to instructions in Section 10.3.1.7.

- Perform PSFS
- Collect PK samples from subset of subjects as described in Section 10.3.2.1

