13.1.4 Efficacy Analysis

13.1.4.1 Primary Efficacy Endpoints

Statistical analysis of efficacy will be assessed by an improvement in the composite SSS (See SAP for SSS scale; Individual Category Severity Assessments: Pulmonary, Cardiovascular, Hematologic Symptoms, Renal, and Nervous Systems) from Baseline (pre-dosing) to 6 and 9 hours after first dose, where the average of the 6- and 9-hour scores are used as the post treatment value: Change = (Baseline – [6hr + 9hr]/2). Subjects that die before recording a 6 or 9 hour SSS measurement will be assigned the worst possible score when analyzing the primary endpoint. Missing measurements of the SSS at 6 or at 9 hours won't be replaced for the purpose of calculating the primary outcome. If the SSS at one of these timepoints is missing, the average SSS will be based solely on the SSS recorded for the other time point.

13.1.4.2 Secondary Efficacy Endpoints

The secondary efficacy endpoints are to evaluate the:

- AUC of the pulmonary, cardiovascular, hematologic symptoms, renal, and nervous system sections of the SSS from Baseline through Day 7
- Complete SSS from Baseline through Day 7
- SSS neurologic system subscore from Baseline through Day 3
- Coagulation abnormalities from Baseline through Day 7
- Hemolysis markers from Baseline through Day 3
- Levels of the myonecrosis marker, creatine kinase (CK), from Baseline through Day 3
- Numeric Pain Rating Scale (NPRS) score in patients able to respond from Baseline through Day 28
- Kidney function markers from Baseline through Day 28
- Total differential antivenom requirement from Baseline through Day 28
- Head-Lift duration from Baseline through Day 7
- Total duration of ventilatory support from Baseline through Day 28
- Total duration of Intensive Care Unit (ICU) stay from Baseline through Day 28
- Total duration of hospitalization from Baseline through Day 28
- All-cause mortality from Baseline through Day 28
- Clinical Global Impression-Improvement (CGI-I) from Baseline through Day 7
- Patient Global Impression of Change (PGIC) from Baseline through Day 7
- Patient-Specific Functional Scale (PSFS) total score from Baseline through Day 28

13.1.4.3 Exploratory Endpoints

The exploratory efficacy endpoints are to evaluate the:

- Change in the SSS from Baseline through Day 7 using compressed SSS scale
- SSS from Baseline through Day 28 after first dose
- Grip strength pre-dosing through Day 28

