#### 6.1.4.1. Multiple Imputation

The multiple imputation (MI) procedures for the primary and key secondary endpoints are described below.

For the primary analysis, missing data not due to mortality, and not addressed by the averaging rules above, will be imputed using the following regression-based multiple imputation model.

The following imputation algorithm will be applied to each SSS subscore separately, then the primary outcome SSS score will be derived.

1. The first step is to understand the pattern of missingness. In order to perform the multiple imputation, a monotone missing pattern must be achieved. For example, if there exist values for baseline and Day 2 visits, but missing values for the Day 1 (8-10h) visit, Markov-Chain Monte-Carlo (MCMC) method will be used to impute the small amount of missing data that may be missing at the intermediate visits that is required to make the missing data pattern monotone before applying the multiple imputation algorithm. This method uses a non-informative Jeffreys prior to derive the posterior mode from the expectation-maximization (EM) algorithm as the starting values for the MCMC method. This MCMC method will use seed of 432832. To avoid values that could not be observed in practice, imputed values will be constrained to be integers in the range of 0 to 3 or 0 to 4 by convention to align with the scale of the questionnaire. A total of 10 imputations will be done in the MCMC step.
2. Once the monotone pattern is achieved, the next step is to implement the imputation algorithm. For this, the Predictive Mean Matching method (PMM) will be used. This method is particularly helpful if the normality assumption is violated. For subjects with complete data up to a particular visit, a PMM model will be fit that includes the outcome at that visit as the dependent variable; and as independent variables gender, treatment assignment, study site, and non-missing scores using a seed of 931428. This process will be repeated 15 times, resulting in a total of 150 complete analysis datasets.
3. For each completed dataset, any necessary derived variables will be computed. Then the ANCOVA model will be performed for the 6 and 9 hour average SSS score. The results will be combined into one MI inference (LS mean, associated 95% CI, and p-value) using PROC MIANALZE as illustrated (Ratitch et al., 2013).

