#### **6.1.4.3. Tipping Point Analysis**

A sensitivity analysis for the primary endpoint will be performed by creating a table in which each patient who is missing primary outcome data is represented. For each of these patients, all possible values for the primary outcome that go towards the null hypothesis (i.e., decreasing SSS score for Placebo subjects and increasing SSS scores for Varespladib-Methyl subjects) will be examined and the p-value for the primary efficacy endpoint will be recalculated. This analysis will show the range of outcomes for which the results of the primary analysis shift from significant (i.e.,  $\alpha \leq 0.05$ ) to non-significant (i.e.,  $\alpha > 0.05$ ).

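### SAP 6.1.4 fills both-missing primary scores with investigator-determined values without recording a departure from the protocol, and these scores appear to fall outside the tipping-point analysis

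*SAP*

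**What the plan says.** Protocol 13.1.4.1, repeated in Protocol 10.3.1: "Missing measurements of the SSS at 6 or at 9 hours won't be replaced for the purpose of calculating the primary outcome". If one of the two scores is missing, "the average SSS will be based solely on the SSS recorded for the other time point". The only value the protocol assigns is the worst score for a patient who dies. It has no separate rule for a survivor with neither score.

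SAP 6.1.4 keeps the one-missing rule. When both are missing, "the site investigator will be asked to use all available contemporaneous clinical and laboratory data to determine the SSS at these time points". The safeguard is timing: "These scores will be obtained and finalized prior to database lock to ensure that investigators are blinded during this process". Only then, "if missing data persists after the prior methods, then multiple imputation will be performed".

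SAP 6.1.4.1 restates the scope of imputation as "missing data not due to mortality, and not addressed by the averaging rules above", without mentioning the investigator step. SAP 6.1.4.3 builds the tipping-point analysis by "creating a table in which each patient who is missing primary outcome data is represented". SAP 6.1.4 names that analysis as the missing-data sensitivity analysis for the primary endpoint.

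**The concern.** There are two problems.

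First, the protocol's sentence against replacement is general, and on its face it covers a patient missing both scores. The SAP supplies a value for such a patient by two successive routes. Its Document History and Section 10 describe what changed between SAP versions, including the addition of multiple imputation. Neither says that filling these scores departs from the protocol.

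Second, once the investigator has supplied a score, the patient no longer looks missing. The score then enters the ANCOVA with the same standing as a bedside assessment. It carries no imputation variance, and on the natural reading the tipping-point table does not vary it. The more gaps investigators fill, the smaller that table becomes, and the more robust the result will appear.

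The primary estimand in SAP 2.2.1.1 is framed on observed values, SAP 4.1 calls the study confirmatory, and the primary test gates all four key secondary endpoints (SAP 8.1.2). A claim that the primary result is robust to missing data should therefore cover every patient whose score was not recorded at the time.

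**Working it through.** **Order of steps for a survivor with neither score**

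1. Averaging rule: does not apply, because there is no score to use.
2. Investigator determination (SAP 6.1.4): if it succeeds, a 6-hour and a 9-hour score now exist.
3. Multiple imputation: conditional on data remaining missing, so it is skipped.
4. Tipping point (SAP 6.1.4.3): conditional on missing primary outcome data, so it is skipped if missing means still missing.

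Step 4 is an inference. SAP 6.1.4.3 does not say whether missing means never recorded or still missing, and SAP 6.1.4.1, taken alone, would send this patient to imputation.

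The other primary sensitivity analyses in SAP 8.1.1 are rank regression, the antivenom covariate, the compressed SSS and leaving out one site at a time. Neither these nor the per-protocol repeat flags, varies or specifically excludes investigator-determined scores.

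**The plan's own figure**

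Inputs (SAP 3.2): difference 1.1, SD 1.75, two-sided alpha 0.05, power 85%, ratio 1:1. The normal formula gives 46 per arm, or 92. The two-sample t-test gives 84.7% power at 92 and 85.4% at 94. The stated 94 reproduces, so sample size is not at issue.

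**Size of the effect**

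The documents do not give the number missing both scores or the likely scoring error. I assume k patients in one arm, each with error e in the same direction. Patients scored by the investigator stay in the analysis, and the 15% withdrawal rate runs to the end of the study rather than to 9 hours. I therefore use 110/2 = 55 per arm. Shift in the treatment difference = k × e / 55:

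| k | e = 1 | e = 2 | e = 3 |
|---|---|---|---|
| 1 | 0.018 | 0.036 | 0.055 |
| 2 | 0.036 | 0.073 | 0.109 |
| 3 | 0.055 | 0.109 | 0.164 |
| 5 | 0.091 | 0.182 | 0.273 |

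Against the target, 0.018/1.1 is about 2% and 0.273/1.1 is about 25%.

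**When this could change the conclusion**

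With N = 110 and SD 1.75, the standard error is 1.75 × √(4/110) = 0.334, and the smallest significant difference is about 0.661 (unadjusted t-test, an approximation to the ANCOVA). Total error needed in one arm to lose significance = (observed difference − 0.661) × 55:

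| Observed difference | Points needed | Patients at 3 points each |
|---|---|---|
| 0.7 | 2.1 | 1 |
| 0.8 | 7.6 | 3 |
| 0.9 | 13.1 | 5 |
| 1.1 | 24.1 | 9 |

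**What a no-replacement analysis would cost in power**

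Dropping m unscored patients from 110, at a true difference of 1.1, gives power of 90.4% (m = 0), 89.1% (m = 5), 87.5% (m = 10) and 85.4% (m = 16, which leaves 94).

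**The case against.** The sponsor has a fair reply.

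- **No rule for this case.** The protocol's sentence leads straight into the one-missing rule, which the SAP keeps. For both missing, the protocol gives no specific instruction, defines ITT as all randomized patients (13.1.1), and leaves detail to the SAP (7.1, 13.1.4.4).
- **Late scoring, not replacement.** The protocol foresees that "clinical evaluation of the actual SSS point score will be performed after completion of the study". Appendix B scores the hematologic and renal systems largely from laboratory values and urine output, and gives numeric heart-rate and respiratory-rate bands. Protocol 10.3.1 also has acute changes in the first 24 hours recorded as unscheduled visits.
- **Blinding and site checks.** Scoring is finished before database lock, and leaving out one site at a time partly guards against one site's scoring habits.

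Much of this stands. It supports keeping investigator scoring in the primary analysis, and it means subscores fixed by measured values should not be treated as unknown. It does not remove the point. Deferred scoring covers assessments that were carried out, and Protocol 10.3.1.1 asks for each subscore to be recorded, with a justification, at each timepoint. The SAP step concerns scores that are absent. Nervous-system items and some pulmonary items depend on bedside judgement that laboratory results cannot restore. Blinding limits bias by arm, but it does not remove scoring error or the false precision of treating a later determination as observed.

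**Conclusion.** The point holds as a gap in reconciliation and in sensitivity analysis. It does not show that the primary analysis is biased. The SAP adds two replacement steps that the protocol's wording rules out and does not record the departure. On the natural reading, investigator-determined scores escape the one missing-data sensitivity analysis named for the primary.

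The 0.02 to 0.27 point range rests on assumed k and e, with all error in one arm and one direction. Blinded scoring gives no reason to expect that pattern, so the range is a worst-case illustration. It matters mainly for a borderline result.

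A reader might infer more than the documents support:

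- **That the tipping-point analysis never tests these scores.** SAP 6.1.4.3 leaves missing undefined and SAP 6.1.4.1 omits the investigator step, so exclusion is likely but not stated. Any values that are multiply imputed do carry imputation variance and do enter the table.
- **That the two documents assign different primary values to the same patients.** For survivors missing both scores, the protocol assigns none.
- **That emergency unblinding undermines the scoring.** Protocol 9.6 permits it in a medical emergency and otherwise discourages it. The concern would need a broken code and both scores missing in the same patient, and nothing in the documents suggests how often that would occur.

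**What to change.** - Reconcile the protocol and SAP wording on replacement, and record the departure in SAP Section 10, covering both the investigator step and multiple imputation.
- Flag every investigator-determined 6- or 9-hour score and report the count by arm.
- In SAP 6.1.4.3, define the set as all surviving patients with no SSS recorded at either visit at the time, including those later scored by the investigator. Hold fixed any subscore that follows directly from measured laboratory or vital-sign values, and vary the rest.
- Name the investigator step in SAP 6.1.4.1 so that the two sections agree.
- Add a named sensitivity ANCOVA without replacement, as the protocol states.

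The cost is one data flag, one extra model run and SAP wording. No new data are needed.

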The first key secondary analysis on AUC will use the same process above, except in step 3 the AUC will be derived for each subject in each imputed dataset, then analyzed and aggregated as above using PROC MIANALZE (Ratitch et al., 2013).

The secondary key secondary analysis on antivenom amounts will not use multiple imputation.

The third key secondary analysis on NPRS AUC will use the same process above, except in step 3 the NPRS-AUC will be derived for each subject in each imputed dataset, then analyzed and aggregated as above using PROC MIANALZE (Ratitch et al., 2013).

The fourth key secondary analysis on CGI-I will use the same MI method described above, except using baseline and post-baseline CGI-I scores.

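### CGI-I at Day 2 and NPRS-AUC through Day 3 have no rule for death, so the SAP as written imputes dead patients from living ones

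*SAP*

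**What the plan says.** **Death on the SSS.** Protocol 10.3.1.1 gives a death the maximum in every SSS section. SAP 2.2.1.1 assigns the worst score in the primary estimand, and SAP 6.1.7.1 sets it at 16. SSS-AUC can rely on the protocol's section rule.

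**The third and fourth key secondaries.** For NPRS-AUC through Day 3, SAP 6.1.4 says "multiple imputation will be used to replace missing scores based on country, baseline age, gender, baseline NPRS scores" (treatment and later scores are added to the list). For CGI-I it says "For the fourth key secondary endpoint, CGI-I at Day 2, multiple imputation will be used to model missing values". SAP 6.1.4.1 adds "The third key secondary analysis on NPRS AUC will use the same process above" and "The fourth key secondary analysis on CGI-I will use the same MI method described above, except using baseline and post-baseline CGI-I scores".

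**Where deaths are kept out of imputation.** The only such clause opens with the primary analysis: "For the primary analysis, missing data not due to mortality, and not addressed by the averaging rules above, will be imputed". In the imputation step itself, "the Predictive Mean Matching method (PMM) will be used". The code in SAP 6.1.4.2 has no filter for deaths. The derivation and analysis sections for the two endpoints (SAP 6.1.7.3, 8.1.2.3, 8.1.2.4) and their code (8.1.3) do not mention death.

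**Patients unable to respond.** The opening of Protocol Section 10 lists CGI-I and NPRS among the assessments a patient may be unable to answer and refers to 10.3.1. That section gives the worst available score when the cause is severity of envenoming, but lists values only for PSFS, PGIC and grip strength. The SAP version is narrower: "Individuals who cannot respond to patient-reported assessments due to severity of snakebite envenoming will be given a score corresponding to the worst score available". It lists the same three values.

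**The concern.** SAP 4.1 calls the study confirmatory, and these two endpoints are tested formally in the fixed sequence. Predictive mean matching takes its value from a patient who was assessed at that visit, and therefore alive. A death before Day 2 would enter the CGI-I model with a survivor's rating, while the same death counts as the worst outcome on the primary endpoint and SSS-AUC. If the mortality clause is instead read across through the reference to the same process, the patient has no value and drops out, although SAP Section 5 defines ITT as everyone randomized and uses it for all efficacy analyses. Two programmers could follow the text and build different datasets.

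The planned checks would probably not show this. The missing-data sensitivity analysis for key secondaries starts only when results cannot be calculated for more than 10 participants, and its form is chosen on review of the data (SAP 6.1.4). The tipping-point analysis covers only the primary endpoint (6.1.4.3). The mortality model is not run with fewer than 5 deaths (8.2.12).

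**Working it through.** **Plan figures, reproduced first.** Five-section maximum: pulmonary 3 + cardiovascular 3 + hematologic 4 + renal 3 + nervous 3 = 16, as in SAP 6.1.7.1. Sample size: difference 1.1, SD 1.75, two-sided 5%, 47 per arm gives 85.4% power by t-test, so 94 is confirmed. No stated figure is in dispute.

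**Who is affected.** The Day 2 assessment falls 12 to 18 h after the 8–10 h assessment (Protocol Table 1, note d; SAP 6.1.7.15). Hence 8 + 12 = 20 h to 10 + 18 = 28 h after first dose. For CGI-I only deaths before then matter. For NPRS-AUC only deaths before 48 h matter, because the Day 3 score is set at 48 h (SAP 6.1.7.3).

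**CGI-I, one excess death in one arm.** Inputs: 110/2 = 55 per arm (Protocol 13.2); worst value 7 (Protocol 10.3.1.2). Assumed, because the documents do not give them: SD 1.0 to 1.3, mean m of the other 54 patients in the arm, and imputed value v.

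- Shift in arm mean = (7 − v)/55
- Variance in that arm, s₁² = [53·SD² + (54/55)(7 − m)²]/54
- SE of the difference between arms = √[(s₁² + SD²)/55]

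| Imputed value | m | SD | Shift | SE | Shift/SE |
|---|---|---|---|---|---|
| Typical survivor, v = 2 | 2 | 1.0 | 5/55 = 0.091 | 0.210 | 0.43 |
| Typical survivor, v = 3 | 3 | 1.3 | 4/55 = 0.073 | 0.257 | 0.28 |
| Poor survivor, v = 4 | 2.5 | 1.0 | 3/55 = 0.055 | 0.207 | 0.26 |
| Poor survivor, v = 5 | 2.5 | 1.3 | 2/55 = 0.036 | 0.260 | 0.14 |

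First row in full: s₁² = [53 + (54/55)·25]/54 = 1.436, and √[(1.436 + 1)/55] = 0.210.

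With two excess deaths the four rows become 0.80, 0.55, 0.49 and 0.27 SE. With 47 per arm and one death they become 0.46, 0.30, 0.28 and 0.15.

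**NPRS-AUC, under one possible convention.** Suppose 10 is carried from death at time t to 48 h, instead of an imputed level L. The arm mean then moves by (48 − t)(10 − L)/55 point-hours.

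- t = 6 h, L = 3: 42 × 7/55 = 294/55 = 5.35; SE 19.0 (time-averaged SD 2.0 assumed); 0.28 SE.
- t = 24 h, L = 5: 24 × 5/55 = 120/55 = 2.18; SE 22.9 (SD 2.5 assumed); 0.10 SE.

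The SEs ignore covariate adjustment.

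**The case against.** The strongest reply is that the protocol already points to an answer. Section 10 names CGI-I and NPRS, and 10.3.1 gives a worst-score rule that is not limited to patient-reported scales. This stands in part: it shows the direction the protocol leans. It does not close the gap, because neither place mentions death or lists a value for either scale. The SAP also narrows the rule to patient-reported assessments, which leaves out the clinician-rated CGI-I, and sends missing scores to imputation.

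The small size also stands. The window is about one to two days. SAP 8.2.12 provides for fewer than 5 deaths over 28 days. Imputation uses earlier CGI-I scores, scheduled at 1, 2, 3–4, 5–6 and 8–10 h, so a patient seen to worsen would be matched to a poor survivor. That makes 0.14 to 0.26 SE the more realistic range. NPRS-AUC is tested only after three rejections and CGI-I only after four.

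It is also fair to say that pain after death has no natural value. The choice of NPRS convention is a judgement; the defect is that none is stated.

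A reader might infer three stronger things that the documents do not support:

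- That the SAP means to drop deaths from the ITT test. The exclusion is worded for the primary, and SAP 6.1.4 prescribes imputation without exception, so imputation is the literal reading.
- That hospital and ICU stay share the flaw because an early death would count as a short stay. No passage says that death is entered as discharge. These endpoints are exploratory (SAP 8.2), and ranking death beyond the longest stay would be a design choice.
- That antivenom defaults to the lowest category after a death. Vials given up to death are an observed count. For data missing before Day 3 in a patient who "has not been discharged from the hospital or is transferred to another hospital, we will review each case", the SAP already has a route.

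**Conclusion.** The point holds for CGI-I at Day 2 and NPRS-AUC through Day 3, and its severity is minor. The text applies imputation to all missing scores on both endpoints, so an early death gets a living patient's value; reading the primary's exclusion across removes the patient instead. Both outcomes conflict with how the SSS treats death, and neither is reconciled with the protocol's worst-score rule.

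The effect depends on an imbalance in early deaths, for which the documents give no rate. Under the stated assumptions, one excess death is worth 0.14 to 0.26 SE on CGI-I against a matched poor survivor and at most 0.43 SE against a typical one. That is small beside the 1.96 SE needed for significance, and remains limited with two deaths. It does not threaten the primary result. Deaths stay visible elsewhere: they are listed, and fatal treatment-emergent events are tabulated by arm (SAP 8.2.12, 9.1, 9.1.2). The reason to act is that the rule is cheap to state now and would look chosen after the fact if settled once deaths by arm are known.

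**What to change.** Before unblinding, in SAP 6.1.4 and 6.1.4.1:

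1. Assign CGI-I = 7, the scale's worst value, to deaths before the Day 2 assessment.
2. Extend the mortality exclusion so that deaths are not imputed from survivors for CGI-I or NPRS-AUC, and add the matching filter to the code in 6.1.4.2.
3. State one NPRS convention for deaths before 48 h, for example the worst score from death onward or an average while alive, with the other as a sensitivity analysis.
4. Reconcile these rules with Protocol Section 10 and 10.3.1, saying whether the rule for patients unable to respond covers CGI-I and NPRS in living patients.
5. Show deaths by arm beside both endpoints.

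No change is needed to the hospital-stay, ICU-stay or antivenom analyses on this account.

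The cost is a few sentences and a simple derivation, with no new data and no change in sample size. The downside is that CGI-I at Day 2 becomes a composite with death and must be labelled so; the same applies to NPRS-AUC if the worst-score convention is chosen.
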